Subjects must not have nephrocalcinosis, renal stones of any type, hydronephrosis, a history of long bone fractures, indwelling hardware, or abnormalities of the skeleton or spine. Subjects must not have congenital glaucoma, known ocular deficits, or clinically relevant abnormalities on renal ultrasound or DEXA scans. Subjects must not have a known history of disturbances of autonomic function, inborn errors of metabolism, mitochondrial dysfunction, or prior evidence of hyperammonemia. Subjects must not have any clinically significant abnormality in laboratory tests at screening, including a bicarbonate level <20 mEq/L, have a diagnosis of metabolic acidosis, or be on alkali therapy.

Caregivers of the subjects must be able to accurately maintain the subject take-home record and seizure diary.

DOSAGE AND ADMINISTRATION

Subjects will be randomly assigned to receive unblinded, flexible dosages of topiramate or levetiracetam as follows:

- Topiramate: weight-based dosing for subjects 2 to <10 years of age, not to exceed 350 mg/day, as tolerated; dosage for subjects 10 to 15 years of age not to exceed 400 mg/day, as tolerated
- Levetiracetam: weight-based dosing for all subjects 2 to 15 years of age, not to exceed 60 mg/kg/day, as tolerated. The maximum recommended daily dosage is 3,000 mg (1,500 mg BID).

Subjects will receive study drug in a twice-a-day regimen. After randomization, subjects will be titrated as tolerated to the maximum recommended dosage for optimal clinical effect over 6 to 8 weeks and will be maintained on that dosage through the open-label treatment phase, with the option for dosage adjustment as required for optimal clinical effect. Changes to this schedule will be based on a risk-benefit

assessment of the subject's clinical condition by the investigator. All study drugs will be provided in child-resistant packaging during the study.

Subjects are recommended not to exceed maximum recommended maintenance dosages; however, subjects will not be discontinued from the study if higher dosages are required for optimal clinical effect as judged by the investigator. Data collected while on dosages that exceed maximal recommendations may be analyzed separately, as appropriate.

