Only AED monotherapy will be used for both treatment groups. However, subjects will not be discontinued from the study if 1 or more concomitant AEDs are added after initiating treatment with study drug. Data will be collected prior to the use of the concomitant AED(s) for the primary analysis. Data subsequently collected while on the concomitant AED(s) will be analyzed in a secondary analysis for each safety outcome of interest.

PHARMACOKINETIC EVALUATIONS

Blood samples (1 mL per sample) for the determination of plasma topiramate and levetiracetam concentrations will be obtained during clinic visits according to the Time and Events schedule. If possible, blood samples for pharmacokinetic (PK) evaluations should be trough samples (ie, taken immediately before the morning dose) and coincide with samples drawn for clinical laboratory tests. During each PK assessment, the dosing regimen, dose administered, time and date of dose administration, time of sample collection, and concomitant medications will be recorded in the case report form.

Pharmacokinetic parameters will not be estimated. Topiramate and levetiracetam plasma concentration data will be summarized.

SAFETY EVALUATIONS

Safety evaluations will include:

- 12-lead electrocardiogram (screening only)
- Vital signs (including orthostatic vital signs), body weight, and height (all visits except Month 2)
- Neurologic and physical examinations (all visits except Month 2)
- Physical activity evaluation (screening)
- Clinical laboratory tests (screening, Month 1, Month 3, Month 6, Month 9, and Month 12/early withdrawal)
- Pregnancy testing (for girls of childbearing potential; serum at screening only; urine at all other visits)
- 24-hour urine collection (Screening, Month 6, and Month 12/early withdrawal)
- Adverse event monitoring, concomitant medication monitoring (throughout)
- Suicidality, as assessed by the Columbia Suicide Severity Rating Scale (C-SSRS; all visits except screening)
- DEXA scan (baseline, Month 6, and Month 12/early withdrawal)
- Renal ultrasound, biochemical bone markers (screening, Month 6, and Month 12/early withdrawal)
- Bone age, as determined by hand/wrist x-ray (baseline and Month 12/early withdrawal)
- Tanner staging of subjects of age 8 years and above (baseline, Month 6, and Month 12 or early withdrawal)
- Seizure counts recorded by parent/guardian in take-home seizure diary (all visits beginning at baseline)

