Hyperchloremic, non-anion gap, metabolic acidosis (ie, decreased serum bicarbonate below the normal reference range in the absence of chronic respiratory alkalosis) is associated with topiramate treatment. This metabolic acidosis is caused by renal bicarbonate loss due to the inhibitory effect of topiramate on carbonic anhydrase. Such electrolyte imbalance has been

observed with the use of topiramate in placebo-controlled clinical studies and in the post-marketing period. Generally, topiramate-induced metabolic acidosis occurs early in treatment, although cases can occur at any time during treatment. Bicarbonate decreases are usually mild to moderate (average decrease of 4 mEq/L at daily dosages of 400 mg/day in adults and at approximately 6 mg/kg/day in children); rarely, subjects can experience severe decreases, to values <10 mEq/L.³³

Some manifestations of acute or chronic metabolic acidosis may include hyperventilation, nonspecific symptoms such as fatigue and anorexia, or more severe sequelae, including cardiac arrhythmias or stupor. Chronic, untreated metabolic acidosis may increase the risk for nephrolithiasis or nephrocalcinosis, and may also result in osteopenia or osteoporosis, with an increased risk for fractures. Chronic metabolic acidosis in pediatric subjects may also reduce growth rates. A reduction in growth rate may eventually decrease the maximum height achieved. The effect of topiramate on growth and bone-related sequelae has not been systematically investigated.

Growth and Maturation

Reports have suggested that certain AEDs may adversely affect growth and maturation in some children. Body weight was evaluated among pediatric subjects 6 to 15 years of age in clinical studies with topiramate monotherapy, and in 1 of these studies (study TOPMAT-EPMN-106) body mass index (BMI) was evaluated according to Centers for Disease Control (CDC) criteria. Among pediatric subjects administered topiramate monotherapy in studies TOPMAT-EPMN-104, TOPMAT-EPMN-105, and TOPMAT-EPMN-106, mean body weight increased in the double-blind treatment phase; most subjects experienced an increase or no change in body weight. Of those with weight loss, most exhibited decreases of 1% to 9%. Adverse events of weight loss were reported in 21% of pediatric subjects but none was serious or treatment-limiting. In the open-label extension of monotherapy treatment studies TOPMAT-EPMN-104 and TOPMAT-EPMN-106, mean body weight of pediatric subjects also increased.

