13. Subject has clinically relevant abnormalities noted on renal ultrasound or DEXA scans. Subjects with baseline BMD Z-scores ≤ -2 , for either posterior-anterior lumbar spine (L1-L4) or total body less head, will not be enrolled.
14. Subject has congenital glaucoma or known ocular deficits, or is receiving any ocular medications except lubricating eye drops or topical antibiotics.
15. Subject has a known history of central hyperthermia, dysautonomia, or other disturbances of autonomic function.
16. Subject has a known history of inborn errors of metabolism, mitochondrial dysfunction, or prior evidence of hyperammonemia.

-
17. Subject has any clinically significant abnormality in laboratory tests at screening, including but not limited to:
 - WBC count $<3,000/\mu\text{L}$ or absolute neutrophil count $<1,000/\mu\text{L}$ in the last 6 months
 - Aspartate aminotransferase (AST), alanine aminotransferase (ALT), or gamma-glutamyltransferase (GGT) ≥ 3 times the ULN
 - Total bilirubin ≥ 1.5 mg/dL or conjugated bilirubin $\geq 20\%$ of total
 - Venous ammonia ≥ 2 times the ULN
 - 25-hydroxy-vitamin D (level for clinically significant vitamin D deficiency is <12.0 ng/mL, conventional units [<30 nmol/L, SI units])^{19,42}
 - Parathyroid hormone (normal reference range is 14.0 to 72.0 pg/mL)
 - 1,25-dihydroxy-vitamin D, as determined by the age-dependent reference ranges (see lab manual)
 - Insulin-like growth factor 1 (IGF-1), as determined by the age-dependent reference ranges (see lab manual)
 18. Subject has a bicarbonate level <20 mEq/L, has a diagnosis of metabolic acidosis, or is on alkali therapy.
 19. Subject has refractory epilepsy and requires adjunctive AED therapy or is receiving >1 concurrent AED (including benzodiazepines, regardless of the reason for prescription).
 20. Subject is being treated with furosemide, hydrochlorothiazide, vigabatrin, vitamin B₆ therapy for epilepsy, monoamine oxidase (A or B) inhibitors, felbamate, zonisamide, or any other medication that is a potent carbonic anhydrase inhibitor (eg, acetazolamide). Past treatment with furosemide for more than 2 weeks must be discussed with the sponsor and the discussion documented.

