9. STUDY EVALUATIONS

9.1. Study Procedures

9.1.1. Overview

The Time and Events Schedule that follows the synopsis summarizes the frequency and timing of safety, PK, and other measurements applicable to this study.

The study includes 3 phases: a screening phase of up to 35 days, an open-label treatment phase of 1 year's duration (including titration and maintenance), and a posttreatment phase of 30 days, during which subjects will either continue on commercially available topiramate or levetiracetam or will be tapered off of topiramate or levetiracetam over a period of up to 2 weeks. There may be an optional post-study follow-up phase to obtain DEXA measurements in a subgroup of subjects who experience a clinically important reduction (change in Z-score of -0.5 or greater) in BMD, based on local DEXA scan results, after 1 year of treatment with topiramate, to determine whether a decrease in BMD after or during 1 year of treatment with topiramate is reversible. These subjects will have a repeat DEXA scan 6 months after discontinuation of study drug.

The total blood volume to be collected from each subject will be approximately 44.7 mL (45.8 mL for adolescent girls who require serum pregnancy test at screening; [Table 2](#)). Blood samples for testing specific analytes are listed in order of priority, in the event of difficulties in obtaining the desired volume of blood for any reason at a specific visit. Repeat or unscheduled samples may be taken for safety reasons or for technical issues with the samples.

Table 2: Volume of Blood to be Collected From Each Subject (mL)

Visits	Screening ^a	Month 1	Month 3	Month 6	Month 9	Month 12	Total Volume of Blood ^b
Blood chemistry profile, including electrolytes	1.1	1.1	1.1	1.1	1.1	1.1	6.6
CBC (EDTA whole blood)	1.2	1.2	1.2	1.2	1.2	1.2	7.2
25-hydroxy-vitamin D ^c	1.1			1.1		1.1	3.3
IGF-1 ^c	1.1			1.1		1.1	3.3
Parathyroid hormone (intact) ^c	1.1			1.1		1.1	3.3
1,25-dihydroxy-vitamin D ^c	3.0			3.0		3.0	9.0
Ammonia, venous ^c	1.2	1.2	1.2	1.2	1.2	1.2	7.2

Table 2: Volume of Blood to be Collected From Each Subject (mL)

Visits	Screening ^a	Month 1	Month 3	Month 6	Month 9	Month 12	Total Volume of Blood ^b
Pharmacokinetic samples (plasma; AED levels)		1.2	1.2	1.2		1.2	4.8
Serum pregnancy test	1.1						1.1
Total	10.9 mL	4.7 mL	4.7 mL	11.0 mL	3.5 mL	11.0 mL	45.8 mL

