5	Month 3	76 to 135	90
6	Month 6	136 to 225	180
7	Month 9	226 to 315	270
8	Month 12	>=316	360

^a The randomization day is Day 1.

The analysis windows for DEXA is given in [Table 8](#).

Table 8: Definition of windows for DEXA:

Scheduled Visit Number	Time Interval (label on output)	Time Interval (Day) ^a	Target Time Point
1, 2	Baseline	-35 to 30	1
6	Month 6	31 to 270	180
8	Month 12	>=271	360

^a The randomization day is Day 1.

The analysis windows for Pharmacokinetics is given in [Table 9](#).

Table 9: Definition of windows for Pharmacokinetics

Scheduled Visit Number	Time Interval (label on output)	Time Interval (Day) ^a	Target Time Point
3	Month 1	2 to 45	30
5	Month 3	46 to 135	90
6	Month 6	136 to 270	180
8	Month 12	>=271	360

^a: The randomization day is Day 1

Baseline is defined as the last non-missing observation (including an unscheduled visit) prior to or equal to Day 1 (except for DEXA and Bone age, where baseline includes up to 30 days and 180 days post-baseline, respectively).

For post baseline observations, if more than one visit (including an unscheduled visit) occurs in the same time window, the visit nearest to the target day will be used in the analysis. In the case of an equal distance in time, the latest visit will be used.

Data that are not used in the analysis due to multiple observations or being excluded from the above defined time intervals will be displayed in the data listing.

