5. SUBJECT INFORMATION

5.1. Demographics and Baseline Characteristics

Subject demographics and baseline disease characteristics will be listed and summarized for the randomized analysis set by treatment group. Descriptive statistics (mean, standard deviation, median, minimum, and maximum) will be presented for age, height, weight, body mass index (BMI), and years since diagnosis of epilepsy. Frequency counts and percentages will be presented for categorical variables sex, age group (2-5 years, 6-9 years, 10-12 years, 13-15 years), ethnicity, race, geographic region, seizure types present within the last 2 years, seizure occurred within the last 2 years beyond 3 or 5 month, seizure occurred in last 3 or 5 months and any AED drug/therapy at study entry and bicarbonate categories. Bicarbonate values are categorized as low (<20 mEq/L at screening) and non-low bicarbonate values (\geq 20 mEq/L at screening).

Age in years will be used from eCRF. In case of missing eCRF for age, 15th of the month will be used as day. Missing day and month at date of birth will be imputed by June 30. Years since diagnosis of epilepsy will be calculated based on year of Day 1 minus year of diagnosis (if both in the same year it will be 0).

- Age calculation:
 - For Height and Weight Z-Scores, it is given in CDC guidance document, age is in month with one decimal.
 - For demographics, it is floor (ICF date minus birth date)/365.25), age is in full years.
 - For Vineland it is floor ((intck ('month', birth date, visit date)-(day (visit date)<day(birth date))))), age is in full month.
 - For CBCL it is floor (visit date minus birth date)/365.25), age is in full years.
 - For Cogstate it is floor (visit date minus birth date)/365.25), age is in full years.
 - For vital signs it is floor (visit date minus birth date)/365.25), age is in full years.
 - For labs it is floor (visit date minus birth date)/365.25), age is in full years.
 - Age for determination of max daily dose for Topiramate or Levetiracetam it is floor (date of dosing minus birth date)/365.25), age is in full years.
- BMI is calculated as weight (kg) / height (m)².

Geographic region will be summarized as North America, South America, Europe and Asia Pacific.

- North America: US, Canada
- South America: Argentina, Mexico
- Europe: Belgium, France, Germany, Hungary, Italy, Poland, Russian Federation, Austria, South Africa, UK
- Asia Pacific: Australia, Taiwan, Philippines

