7.2. Weight

Observed weight values, change from baseline, Z-scores for weight, and change from baseline in Z-scores for weight will be listed and summarized by visit using descriptive statistics. The change in weight z-scores will also be summarized by subject's serum bicarbonate categories.

MMRM analysis will also be performed for changes from baseline and changes in Z-Scores from baseline.

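### SAP 7.2 to 7.4 group growth and bone change by a low-bicarbonate category that the eligibility criteria bar; separately, the SAP's PTH low limits lie inside or above the protocol's normal range

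*SAP*

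**What the plan says.** **Bicarbonate.** SAP 7.2, 7.3 and 7.4 each add a table of Z-score change (weight, height, BMD) by the child's "serum bicarbonate categories". None of the three sections gives a cut-off or a time point. Categories appear only in SAP 5.1: "Bicarbonate values are categorized as low (<20 mEq/L at screening"; the other group is 20 mEq/L or above, also at screening. Protocol 4.2, exclusion 18, reads: "Subject has a bicarbonate level <20 mEq/L, has a diagnosis of metabolic acidosis, or is on alkali therapy". The synopsis puts the test at screening: "Subjects must not have any clinically significant abnormality in laboratory tests at screening, including a bicarbonate level <20 mEq/L". Protocol 1.2 gives particular weight to acidosis caused by topiramate and how it relates to stones, bone density and growth.

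**PTH.** Protocol 4.2, exclusion 17, gives a PTH normal range of 14.0 to 72.0 pg/mL, not split by age. SAP Appendix 2, in its list of additional parameters, sets these markedly abnormal limits:

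| Age | Low (pg/mL) | High (pg/mL) |
|---|---|---|
| 2-7 | <40 | >350 |
| 8-10 | <50 | >490 |
| 11-12 | <70 | >750 |
| 13-16 | <100 | >1100 |

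SAP 7.10 uses the SAP's ranges in place of the central laboratory's and counts a markedly abnormal value only if it was absent at baseline. It also plans a shift table by normal range. SAP 7 recalculates age at each visit to choose the limit.

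**The concern.** The tables in 7.2 to 7.4 are the only ones in the SAP that set growth or bone change against bicarbonate. Acidosis from topiramate arises on treatment: Protocol section 1 reports an "average decrease of 4 mEq/L at daily dosages of 400 mg/day in adults and at approximately 6 mg/kg/day in children". A category fixed at screening, in a trial that excludes low values at screening, leaves one group and says nothing about that fall.

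The PTH limits raise a different problem. If a markedly low limit sits within the normal range, normal values are flagged, and the rule that a flag must be absent at baseline then hides some changes and creates others. For PTH, 25-hydroxy-vitamin D, 1,25-dihydroxy-vitamin D and IGF-1, Appendix 2 gives markedly abnormal limits but no normal range, so the planned shift table has no classes for these four.

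**Working it through.** **Part (a): who can be in the low group?** The documents state no figure to reproduce, so the check sets the rules side by side.

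1. Eligible at screening: bicarbonate of 20 or more. Low in SAP 5.1: below 20 at screening. No value satisfies both.
2. Repeat samples. Protocol 9.1.1 says "Repeat or unscheduled samples may be taken for safety reasons or for technical issues with the samples", so a child could have a first value below 20 and a later one at or above it. That text does not offer repeats as a way to requalify, and SAP 5.1 does not say which screening sample counts. Under SAP 3.1, "Baseline is defined as the last non-missing observation (including an unscheduled visit) prior to or equal to Day 1", the later value would count and the child would not be low.
3. The reverse case, a qualifying value followed by a pre-dose value below 20, is covered by the note closing Protocol 4.2: a child who stops meeting the criteria before the first dose is excluded.
4. What remains is eligibility deviations. On the last pre-dose value, the number of eligible children in the low group is 0.
5. Data not used. The synopsis lists "Clinical laboratory tests (screening, Month 1, Month 3, Month 6, Month 9, and Month 12/early withdrawal", which is five scheduled visits after baseline. The screening category uses none of them.

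**Part (b): PTH limits against 14.0 to 72.0 pg/mL.** Range width = 72 − 14 = 58.

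| Age | Share of range width below the low limit | High limit ÷ 72 |
|---|---|---|
| 2-7 | (40 − 14)/58 = 45% | 4.9 |
| 8-10 | (50 − 14)/58 = 62% | 6.8 |
| 11-12 | (70 − 14)/58 = 97% | 10.4 |
| 13-16 | 100 exceeds 72, so 100% | 15.3 |

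Consequences under SAP 7.10 and SAP 7:

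- A child aged 13 to 15 with any normal baseline PTH is already markedly low and can never count as a new low.
- An unchanged 60 pg/mL is not low at age 10 (limit 50) but is low at 11 (limit 70), so it counts as new. The newly flagged share of range width is (50 − 40)/58 = 17% on turning 8, (70 − 50)/58 = 34% on turning 11, and (72 − 70)/58 = 3% on turning 13.
- Four times the upper normal limit is 4 × 72 = 288, below the lowest high limit of 350, so it is not flagged at any age.

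A units slip to pmol/L would not resolve the conflict: with the SAP's factor, 40 × 9.434 = 377 pg/mL.

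**The case against.** **On bicarbonate.** A reader might infer that the categories in 7.2 to 7.4 are undefined. The documents do not support that: 5.1 defines bicarbonate categories, the later sections reuse nearly the same phrase for a fixed attribute of the child, and the plain reading is that 5.1 applies. The fault is that the defined low group is empty by design.

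It can also be said that little is lost. SAP 7 plans no formal testing, and acidosis is covered elsewhere: bicarbonate by visit, a markedly low flag at <17, and acidosis adverse events. That stands, and it limits the severity. It does not supply the link between acidosis and growth or bone, which only these three tables attempt.

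A category based on post-baseline values has weaknesses too. It is post-randomization, a child can change group between visits, and an average that includes Month 1 takes in the titration period. These are reasons to state the choice and label it, not to keep a category with one group.

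**On PTH.** The issue is unrelated to bicarbonate and would rate lower alone. A reader might conclude that the row is a proven transcription error. Its high limits are 7.0 to 7.9 times the IGF-1 high limits just above, but the low-limit ratios run from 4.7 to 6.7 and the younger age bands differ. That justifies a check, no more. The high limits are remote from the normal range but do not contradict it.

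**Conclusion.** Both parts hold as inconsistencies in the plan as written. Part (a) is the more serious: the low-bicarbonate group has 0 eligible children, so three tables reduce to one group and cannot show the association the protocol emphasises. This assumes that the 5.1 categories carry over, that eligibility is applied as written, and that the last pre-dose value counts. Part (b): the PTH low limits cover 45% to 100% of the normal range's width, reading the row as printed and in pg/mL.

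Those percentages might be read as shares of children. They are shares of range width; the documents give no PTH or on-treatment bicarbonate distribution from which to count children. Nor does the finding reach the trial's main results: the between-arm height, weight and BMD analyses and the observed and change-from-baseline PTH summaries are unaffected. All affected output is descriptive.

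**What to change.** **(a)** Keep the screening category in 5.1 only, and say which screening sample counts. For 7.2 to 7.4, define a category before the tables are run, from post-baseline bicarbonate dated on or before the growth or DEXA assessment, split at the SAP's own limit of 20. The mean or the lowest such value would serve; state which, and over what span. Match by date, not visit label: the DEXA Month 12 window opens at day 271 while laboratory Month 9 runs to day 315, an overlap of 315 − 271 + 1 = 45 days. Show the tables by arm, label them descriptive and non-randomized, and print the actual number of values behind each child's category. A fixed count would mislead, because a DEXA scan on day 31 is labelled Month 6 and may have one earlier value or none, and early withdrawals contribute fewer.

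**(b)** Check the PTH row for a transcription or unit error, and reconcile it with exclusion 17 so that markedly abnormal limits lie outside the normal range. State the normal ranges that the shift table uses for PTH, 25-hydroxy-vitamin D, 1,25-dihydroxy-vitamin D and IGF-1. The protocol already points to the laboratory manual for age-dependent ranges of the last two.

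**Cost.** Edits to SAP 7.2 to 7.4, 5.1 and Appendix 2; three tables, the PTH flags and the shift table for four analytes to reprogram; no new data. The price of (a) is a post-randomization grouping, possibly with few low children on levetiracetam, so it supports description only.
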